1.2 SECONDARY OBJECTIVES

1.2.1 To estimate tumor upgrading and tumor upstaging rates for each study arm.
1.2.2 To determine the safety of the combination therapy.

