High grade non-muscle invasive bladder cancer tends to respond well to BCG and when it does not, there is evidence to suggest an incomplete or inefficient immune response. Given that CEA and MUC-1 are overexpressed in bladder cancer, we hypothesize that PANVAC™ will augment the BCG-induced cytotoxic T lymphocyte response against bladder cancer cells expressing MUC-1 and/or CEA, which will clinically result in a greater disease-free survival rate than BCG alone in patients who have failed at least one previous course of intravesical BCG. We also hypothesize that the PANVAC+BCG group will demonstrate decreased tumor upgrading and tumor upstaging, particularly with regards to invasion of the detrusor musculature, and predict that the combination treatment will not demonstrate greater treatment-related toxicities to intravesical BCG alone. Finally, we hypothesize that the immune response will be augmented in the PANVAC+BCG group compared to BCG alone as measured by secondary immunologic correlates described below.

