Systemic sepsis and even death can also develop early following local instillation of BCG. During the initial clinical experience with BCG as an intravesical agent, most cases of sepsis could be traced back to recognized errors in BCG administration such as traumatic catheterization, administration too early after transurethral surgery, or instillation during a concomitant UTI. All these conditions result in physical disruptions in the urothelial blood barrier. Sepsis has been estimated to occur in approximately one in every 15,000 patients treated with intravesical BCG.³⁴ Prompt recognition and administration of multidrug, antibiotic therapy is necessary if true BCG sepsis occurs.

- 5.4.1 For the purpose of protecting subject safety, we implement the following stopping rule for safety monitoring of subjects who receive the combination therapy.
- 5.4.2 If one subject experiences a grade 5 event, thought to be possibly or probably due to the combination therapy (PANVAC + BCG), the study will be stopped. For grade 3 or 4

events probably related to the investigational agent (PANVAC) and persisting for more than one week and not improving by routine standard of care, the study will be stopped according to the stopping rule described in Section 14.

5.4.2.1 The exceptions to what constitute true adverse events/DLTs are previously noted.

5.4.3 Formal dose escalation/Phase I study is not planned as the TICE BCG doses are consistent with standard of care and the TICE BCG is being administered in an intravesical fashion while the PANVAC™ is given subcutaneously and in doses that have been shown to be safe in multiple Phase I and Phase II studies in a variety of different cancers.

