Patient accrual is targeted at one patient per month during the first 6 months and 2 patients per month afterwards, and follow-up period after completing accrual will be 12 months. The power calculation was based on one-sided log-rank test at 15% significance level. Sample size, power and duration of the study are presented in the table below. With a total number of 49 patients, the power is 84% (see table below). Under this scenario, the expected number of events (recurrence or death) is 40. In order to allow for the possibility of a small number of unevaluable patients, the accrual ceiling will be set at 54 patients.

	Subgroup 1 1-year recurrence-free survival for BCG persistent patients who failed 1 BCG induction course	Subgroup 2 1-year recurrence-free survival for BCG persistent patients who failed 2 or more BCG induction courses	Subgroup 3 1-year recurrence-free survival for BCG naïve patients	Total sample size	Power (%)	Duration of accrual (months)	Expected number of events (recurrence or death)
Treatment benefit	HR=2.277 1-year RFS: BCG alone: 37.5% BCG+PANVAC: 65%	HR=2 1-year RFS: BCG alone: 20% BCG+PANVAC: 44.7%	HR=1.7 1-year RFS: BCG alone: 48% BCG+PANVAC: 65%	49	84	28	40

One interim analysis for futility will be performed according to the stopping procedure.³⁹ Specifically, the interim analysis will be performed when half of the expected events (20) have been observed. At that time, if the observed event rate of the TICE BCG+PANVAC arm is higher than that of the TICE BCG alone arm (i.e. the hazard ratio ≥ 1), we would consider terminating the trial and concluding that an advantage for the BCG+PANVAC regimen has not been established.

For the purpose of protecting patient safety, we implement the following stopping rule for safety monitoring of patients who receive the combination therapy.

If one patient experiences a grade 5 event, thought to be possibly or probably due to the combination therapy, the study will be stopped. For grade 3 or 4 event, the study will be stopped according to the following stopping rule. These adverse events are described in more detail in Section 7.

Number of patients	No. of grade 3 or 4 serious adverse events
3-9	3
10-18	4
19-26	5

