The operating characteristic of the stopping rule was assessed by simulations. Based on 10,000 simulations, the probability of stopping early for an excess of serious adverse event over the course of trial is 0.04 when the serious adverse event rate is at the anticipated level of 6% and 0.94 when the serious adverse event rate is 30%. This is deemed reasonable for protecting patient safety.

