14.2 SECONDARY ENDPOINTS

Using Kaplan-Meier methods, we will estimate the probability distribution of progression-free survival and the time to recurrence. Results will be summarized by point estimates (12 months) with 95% CI. Exploratory analyses of these secondary objectives will compare the two treatment arms using the log rank test. Fisher's exact test will be used to compare frequency distributions of toxicity grades between the two arms.

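### Section 14.2 compares toxicity between arms only with an unordered Fisher test and gives no estimate or interval, which is a weak answer to the prediction that the combination is no more toxic than BCG alone

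*Combined protocol and SAP*

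**What the plan says.** Section 2 (Background) closes its hypotheses with a comparative claim: the investigators "predict that the combination treatment will not demonstrate greater treatment-related toxicities to intravesical BCG alone". Section 1.2.2 sets the related secondary objective, "To determine the safety of the combination therapy", without naming a comparator or a margin.

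The comparative analysis is in Section 14.2: "Fisher's exact test will be used to compare frequency distributions of toxicity grades between the two arms". No significance level, sidedness, margin, effect measure or interval is attached to it. Section 12.1.1.1 says toxicity is tabulated by each patient's worst grade and shown by arm, so the data for a better analysis are already planned.

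Separately, in Section 14.1, "we implement the following stopping rule for safety monitoring of patients who receive the combination therapy". It is triggered by 3 events among patients 3 to 9, 4 among 10 to 18, or 5 among 19 to 26. Its stated stopping probabilities are "0.04 when the serious adverse event rate is at the anticipated level of 6% and 0.94 when the serious adverse event rate is 30" per cent. Section 5.4 describes the grade 3 or 4 events it counts as "events probably related to the investigational agent (PANVAC) and persisting for more than one week" and not improving with routine care. The same section exempts BCG-related effects that resolve once BCG is reduced or delayed and symptoms are managed conservatively.

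**The concern.** A prediction of no greater toxicity is a claim about how large an excess can be excluded. A test of difference does not address that. Its only outcome compatible with the prediction is non-significance, which at this sample size is likely even when toxicity is considerably higher.

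The plan does better elsewhere. Section 14.2 asks for 95% intervals on the Kaplan-Meier estimates, Section 14.3.3 asks for a proportion with a 95% interval per arm alongside Fisher's test for an exploratory CD8 assay, and Section 14.4.2 asks for intervals on response. Comparative toxicity gets a p-value alone.

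Fisher's test on a grade table also treats grades as unordered labels, so it spends power on patterns other than a shift towards worse grades. What is at stake is how useful the safety result will be to whoever plans the next trial of the combination.

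**Working it through.** **Inputs from the plan.** 49 patients, ceiling 54 (Section 14.1); equal allocation (Section 4.3), so 24 and 25 up to 27 and 27 per arm; event rates of 6% and 30% from the stopping-rule simulation (Section 14.1).

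**Assumptions.** Two-sided 5%, since no level is given; 6% as the BCG-alone rate, since the plan gives 6% only for the combination-arm rule. As a sensitivity value, 11% is the grade 3 or higher dysuria rate on BCG in Section 8.1.2.1.

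**Step 1: the plan's own figure.** Checking the rule after every patient from the third, by exact binomial recursion, the stopping probability at 26 patients is 0.035 at a 6% rate and 0.939 at 30%. At 27 patients it is 0.037 and 0.950. The stated 0.04 and 0.94 are reproduced closely. The same recursion at 26 patients gives 0.66 at a 20% rate and 0.41 at 15%.

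**Step 2: power of Fisher's test on grade 3 or higher, yes/no.** Power = Σₐ Σ_b Bin(a; n₁, p₁) · Bin(b; n₂, p₂) · 1[Fisher p ≤ 0.05], where 1 = BCG and 2 = combination, over all 2×2 tables.

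| BCG n / combination n | 30% vs 6% | 20% vs 6% | 30% vs 11% |
|---|---|---|---|
| 24 / 25 | 0.507 | 0.176 | 0.283 |
| 25 / 24 | 0.588 | 0.257 | 0.337 |
| 25 / 25 | 0.494 | 0.169 | 0.267 |
| 26 / 26 | 0.520 | 0.185 | 0.282 |
| 27 / 27 | 0.495 | 0.159 | 0.275 |

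About 44 per arm would be needed for 80% power at 30% against 6%. A four-category Fisher test, closer to the wording of Section 14.2, gives 0.41 to 0.50 for 30% against 6% by simulation under two assumed splits of the lower grades.

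Borrowing the one-sided 0.15 level that Section 14.1 sets for the log-rank test, power is 0.81 to 0.86 for 30% against 6%, but only 0.49 to 0.56 for 20% against 6%.

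**Step 3: what an interval would show.** Take 6/25 against 1/24. Fisher's p is 0.098, and the difference is 24.0 − 4.2 = 19.8 points with a Newcombe 95% interval of −0.5 to +39.6. The p-value alone hides that an excess of nearly 40 points is still compatible with the data. If both true rates are 6%, the approximate half-width is 1.96 × √(2 × 0.06 × 0.94 / 24.5) = 0.133, or about 13 points.

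**Step 4: using the order of the grades.** As an illustration, assume BCG-arm maximum grades 0 to 4 of 10, 40, 35, 12 and 3%, and a proportional-odds shift with odds ratio 3, which moves grade 3 or higher from 15% to about 35%. At 24 and 25 patients, the unordered Fisher test has about 35% power and a two-sided Wilcoxon test about 53 to 55%, with simulation error of one to two points. Both hold their size at about 5%.

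**The case against.** The strongest reply is that the stopping rule already covers serious harm. A reader might infer from Step 2 that about half of trials with a true 30% rate would end in false reassurance. The documents do not support that. The 6% and 30% rates come from the stopping rule, and on its own events the rule halts 0.927 of trials at 30% with 25 combination patients. Only 1 − 0.927 = 0.073 would run to completion, and a halted trial reassures nobody.

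That part stands, but it does not make Section 14.2 adequate. The rule watches one arm and never compares it with BCG. It counts PANVAC-attributed events and leaves out BCG-attributed effects that resolve once BCG is reduced or delayed. Yet the trial's hypothesis is that PANVAC augments the response to BCG. If it also amplifies BCG toxicity, the arm comparison is where that would show. Nor can Fisher's test serve as a second check on the rule's own events: a trial that was not stopped has at most 4 of them, and 4/25 against 0/24 gives p = 0.11.

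Two further replies are fair. The plan nowhere says that a non-significant result will be read as no greater toxicity, and the rates by arm will be tabulated anyway. The power figures also depend on a significance level the plan does not state. Both limit how hard the point can be pressed, but neither supplies an estimate or interval for the difference.

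**Conclusion.** The point holds as a cheap improvement to the analysis, not as a flaw that endangers the trial. The only comparative toxicity analysis is an unordered test of difference with no estimate or interval. At two-sided 5% it has roughly 50 to 59% power for 30% against 6% and 16 to 26% for 20% against 6%. Those figures rest on the assumed level and the assumed 6% BCG-alone rate; at 11% for BCG alone, power for 30% falls to 27 to 34%. The gain from an ordered test, about 35% to 53–55%, is illustrative and depends on the assumed grade distribution and odds ratio.

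Two stronger readings should be avoided. The plan does not call 30% an unacceptable rate; it is one of two rates at which the stopping rule was simulated. Nor do the documents support taking 30 − 6 = 24 points as a non-inferiority margin, because both figures describe a single arm. A one-sided 95% Newcombe upper bound required to fall below 24 points would declare the combination not more toxic 52% of the time at true rates of 15% against 6%, and 30% of the time at 20% against 6%.

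**What to change.** In Section 14.2, replace the Fisher sentence with wording such as: *Maximum toxicity grade per patient will be compared between arms with an exact Wilcoxon (or trend) test. The difference in the proportion of patients with a treatment-related grade 3 or higher event, related to either agent (BCG+PANVAC minus BCG), will be reported with a two-sided 95% Newcombe confidence interval. Any statement that the combination is not more toxic will be based on this interval; a non-significant test will not be taken as evidence of similar toxicity.* State the level and sidedness of the test. No margin is needed for this change; if the sponsor wants one, it should be set and justified separately.

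The cost is wording only: maximum grade by arm is already to be tabulated, and no extra patients or data are required. There are two downsides. The ordered test is less sensitive to differences that are not a shift in one direction. The interval will be wide, roughly ±13 points or more, so the trial may have to report that excess toxicity is not ruled out.

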14.3 EXPLORATORY/CORRELATIVE ENDPOINTS

14.3.1 To characterize the expression of MUC1 and CEA in bladder tumor specimens pre-(week 0) and the change in expression post-vaccination (on tissue obtained between weeks 17-20) for patients treated with TICE BCG+PANVAC™.

14.3.1.1 MUC1 expression will be evaluated using IHC. A positive result is defined if >5% of tumor cells reacted with any intensity. Intensity will be arbitrarily scored on a 4 point scale: 0 (no staining), 1+ (weak staining), 2+ (moderate staining), and 3+ (strong staining). Potential antibody will be clone Ma695 dilution 1:100 (Novocastra, Newcastle upon Tyne, England) but has to be analytically validated using appropriate positive and negative controls prior to use.²²

14.3.1.2 CEA expression in FFPE pre- and post-treatment tissues will be evaluated by IHC. A positive result is defined when the cytoplasmic staining is equal in intensity to glycocalyceal staining. Tumors will be scored as 0 (no signal), 1+ (signal in <25% sampled tumor area), 2+ (26-75% of tumor cells), and 3+ (>75% of tumor cells). The potential antibody will be CD66e (clone 12-140-10; Novocastra, Newcastle upon-Tyne, England; dilution 1:500; Ventana NexES immunostainer; protease digestion).

14.3.1.3 **Statistical Analysis:** For both MUC1 and CEA expression the distributions of IHC staining intensity at baseline and post-vaccination as well as the change in score will be summarized with descriptive statistics. The results will be summarized by calculating the proportion and 95% confidence interval of positive staining tissue samples at baseline and the distribution of pre and post-vaccination combinations (--, -+, +-, ++) characterizing the change with treatment. Results will be presented separately for each treatment arm. The distributions for the two treatment arms will be compared using a chi square test.

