the NIH have developed a poxvirus cancer vaccine therapy called PANVAC™ that has demonstrated therapeutic efficacy against a variety of carcinomas. PANVAC™ consists of a primary vaccination with a replication competent recombinant vaccinia (rV-) viral vector followed by multiple booster vaccinations with a replication-incompetent recombinant fowlpox (rF-) viral vector. These vectors contain transgenes for both TAAs and human T cell co-stimulatory molecules. Although TAAs are weakly immunogenic, a method of disrupting immune tolerance is to introduce TAAs to the immune system through poxviral vectors.¹⁷ Antigen-specific active immunotherapy is designed to generate immune responses, particularly cell-mediated responses, against specific TAAs using vaccines that express one or more of these antigens.

The TAAs in PANVAC™ are epithelial mucin-1 (MUC-1) and carcinoembryonic antigen (CEA) which are altered and overexpressed in many cancers.¹⁸ MUC-1 is a glycosylated transmembrane protein that is overexpressed in almost all human carcinomas. Furthermore, it has been demonstrated that the c-terminus of MUC-1 functions as an oncogene.^{19,20} According to one study, MUC-1 is present in all cases of malignant urothelium, but increased expression is noted with higher grade and stage tumors.²¹ Another study demonstrated MUC-1 expression in 93% of bladder tumors studied.²² CEA is a glycosylated cell surface protein expressed in several tumors as well and in particularly in colorectal, ovarian, bladder, breast, and gastric tumors.²³ CEA is expressed in 76% of high grade tumors and in 59% of pT1 bladder tumors.²⁴

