3 PATIENT SELECTION

3.1 ELIGIBILITY CRITERIA

3.1.1 Inclusion Criteria

- 3.1.1.1 Patients must have histologically confirmed localized high grade (G3) transitional cell carcinoma (urothelial carcinoma) of the bladder that is stage Ta, T1, and/or CIS

confirmed by the Laboratory of Pathology, NCI 90 days prior to study entry. This can be obtained at an outside hospital prior to entry into the study or at the NCI. However, all outside pathology specimens will require that the formalin-fixed paraffin embedded tissues be re-read by the Laboratory of Pathology, NCI. For patients enrolled at collaborating trial sites, diagnosis must be confirmed by the Department of Pathology at the institution where the patient is enrolled on the trial. Pathology can also be reviewed by the Laboratory of Pathology at the NCI if the participating trial site prefers another pathologic evaluation.

- 3.1.1.2 Patients have failed at least one previous induction course of intravesical BCG, defined as histologically confirmed persistent or relapsing tumor present on post-BCG endoscopic evaluation. All BCG failures will be considered for inclusion into the study, including BCG-refractory, -resistant, and -relapsing, as defined in the “Rationale and Background.” For the purposes of the study, “BCG-refractory” and “BCG-resistant” subjects will be considered to have “BCG-persistent” disease.
- 3.1.1.3 Patients who are not currently candidates for radical cystectomy (e.g. patient refuses surgery, comorbidities preclude major surgery, etc.).
- 3.1.1.4 Age ≥ 18 years.

Because no dosing or adverse event data are currently available on the use of BCG in combination with PANVAC™ in patients <18 years of age, children are excluded from this study.

- 3.1.1.5 ECOG performance status ≤ 2 (see Appendix A, Section 17.1).

- 3.1.1.6 Patients must have normal organ and marrow function as defined below:

- absolute neutrophil count	$\geq 1,500/\text{mcL}$
- platelets	$\geq 50,000/\text{mcL}$
- total bilirubin	$\leq 1.5 \times$ institutional upper limit of normal
- AST(SGOT)/ALT(SGPT)	$\leq 3 \times$ institutional upper limit of normal
- estimated GFR (calculated using CKD-EPI equation)	$\geq 30 \text{ mL/min}/1.73 \text{ sq.m.}$

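### The MUC1 positive/negative cut is probably near its ceiling at baseline, so a between-arm chi-square on the four pre/post categories would discard graded change that the plan already records

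*Combined protocol and SAP*

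**What the plan says.** Section 14.3.1 aims to characterise MUC1 and CEA expression before treatment and its change on tissue taken at weeks 17-20. For MUC1, section 14.3.1.1 sets a binary rule: "A positive result is defined if >5% of tumor cells reacted with any intensity". It also records staining intensity on a scale from 0 to 3+. The paragraph closes with a citation to reference 22.

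Section 14.3.1.3 then plans three things:

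- descriptive summaries of the intensity distributions at both times and of the change in score, shown separately by arm;
- the proportion positive at baseline, and the "distribution of pre and post-vaccination combinations (--, -+, +-, ++) characterizing the change with treatment";
- a between-arm test: "The distributions for the two treatment arms will be compared using a chi square test".

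Two other parts bear on how often a baseline tumour will be positive. Section 2 says of one study: "MUC-1 is present in all cases of malignant urothelium, but increased expression is noted with higher grade and stage tumors". It then adds: "Another study demonstrated MUC-1 expression in 93% of bladder tumors studied". The second statement carries reference 22, the same reference as the MUC1 method paragraph. Section 3.1.1.1 restricts entry to "histologically confirmed localized high grade (G3) transitional cell carcinoma".

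**The concern.** A variable that is positive in nearly everyone at baseline has little room to move. With the cut at 5% of cells and any intensity counted, a tumour that starts positive can leave `++` only by losing almost all staining. A partial fall is not seen, and a rise among positive tumours is not seen either.

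MUC-1 is one of the two antigens the vaccine targets, and its change after vaccination is the stated aim. A table that is mostly `++` with a non-significant chi-square could be taken to mean that the antigen did not change, when the categories had little capacity to show change. The 0 to 3+ score has that capacity, but on the natural reading of 14.3.1.3 it takes no part in the between-arm test.

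**Working it through.** The plan gives no sample size, power or expected cell count for this endpoint, so there is no figure of its own to reproduce.

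**Inputs from the documents.** Total sample 49, ceiling 54 (14.1), randomised equally (4.3). Tissue is provided only if available (5.1.3), so the paired number can be well below 49. MUC-1 prevalence is 93% or 100% (section 2).

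**Assumptions.** The 93% applies under the >5% rule. Score 0 is treated as negative and scores 1+ to 3+ as positive. Baseline splits and shifts are illustrative, because the documents give none.

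**1. Baseline negatives.** Expected number = n × (1 − 0.93).

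- 49 tumours: 49 × 0.07 = 3.4.
- One arm of 24: 24 × 0.07 = 1.7. Chance of none = 0.93^24 = 17.5%.
- 13 paired samples in all: 13 × 0.07 = 0.9. Chance of none = 0.93^13 = 39%.

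At 100% positive, the `--` and `-+` cells are empty.

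**2. Increases.** At most 7% of patients can be `-+`. Even 7% in one arm against 0% in the other would reach two-sided p < 0.05 by Fisher's exact test only about 2% of the time with 24 per arm.

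**3. One-step changes that cross the line.** Moves of one grade up or down were taken as equally likely, with 0% or 7% negative at baseline and the positive tumours split evenly, towards weak staining or towards strong staining.

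- Increases: 0-16% cross.
- Decreases: 10% (strong-heavy), 33% (even) or 60% (weak-heavy) cross.
- All changes: 7-34% cross.

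**4. Effect on a between-arm test.** Illustration: baseline 0/1+/2+/3+ of 7/23/35/35%. Intensity falls by 0/1/2 grades in 30/50/20% of patients with PANVAC and in 85/13/2% with BCG alone.

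- Any fall in score: 0.93 × 0.70 = 65.1% against 0.93 × 0.15 = 14.0%.
- Fall to 0, shown as `+-`: 0.23 × 0.70 + 0.35 × 0.20 = 23.1% against 0.23 × 0.15 + 0.35 × 0.02 = 4.2%.

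The categories therefore reduce a difference of about 51 points to about 19. Simulated power (two-sided 5%, Pearson chi-square on non-empty categories, 2,000-3,000 runs per setting; repeat runs agree to within two or three points):

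| Test and assumed baseline | 5+8 pairs | 12+12 | 24+25 |
|---|---|---|---|
| Four-category chi-square, illustration | 10% | 15% | 39% |
| Same, strong-heavy (50% at 3+) | 5% | 7% | 21% |
| Same, even | 13% | 22% | 50% |
| Same, weak-heavy (50% at 1+) | 25% | 40% | 72% |
| Chi-square on change in score, illustration | 44% | 67% | 95% |
| Rank test on change in score, all baselines | about 43% | about 77% | about 97% |

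**5. If the effect is complete loss.** With loss of staining in 40% against 5%, the four-category chi-square has 26%, 46% and 79% power at the three sizes, and the rank test 20%, 51% and 86%.

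**The case against.** Five points can fairly be made for the plan.

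- **The sources' cuts are unknown.** A reader might infer that the cited studies place 93-100% of bladder tumours above the 5% cut. Section 2 does not say so; it reports presence in one study and expression in the other. Reference 22 is cited in the MUC1 method paragraph, which makes a shared cut plausible, but the citation follows the antibody and validation sentence rather than the cut itself. For the study reporting all cases, the documents offer no such link. This stands, and the ceiling remains an inference.
- **Graded change is reported.** A reader might also infer that the plan as a whole misses most changes in MUC1. It does not: 14.3.1.3 summarises the change in score, by arm. This stands, and confines the weakness to the binary table and any test built on it.
- **The test's target is not named.** The same paragraph speaks of distributions for the staining intensities too. If the chi-square is meant for the change in score, power in the illustration is within about ten points of the rank test. This stands as a limit on the size of the gap. The sentence does come after the four-category table, which makes that the natural reading, and an ordinary chi-square on scores would still ignore their order.
- **The scenario matters.** For decreases, the share that crosses the line runs from 10% to 60% depending on the assumed baseline. Complete loss is visible, and the two tests then perform almost alike. This stands.
- **The consequence is small.** The endpoint is exploratory, carries no power claim and feeds no decision rule. This stands and sets the level of the point.

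**Conclusion.** The point holds as a limited one. If baseline positivity is about 93% or more, the MUC1 positive/negative categories start near a ceiling: about 3.4 negatives among 49, almost no room for increases, and no sight of partial falls. On the natural reading of 14.3.1.3, the between-arm chi-square then discards most graded change. With 24+25 pairs its power is about 20-70% across the assumed baselines, against about 97% for a rank test on the change in score.

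The direction was the same at every baseline tried with graded shifts, but the size rests on assumed splits and shifts and on the four-category reading. It nearly vanishes for complete antigen loss and is small if the change score was the intended target. That the categories miss most change is firm only for increases. The documents do not show it for decreases, nor for the plan as a whole. This is a desirable clarification of an exploratory analysis and does not touch the trial's primary conclusions.

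**What to change.** In 14.3.1.3, state that the exploratory between-arm MUC1 comparison is the pre-to-post change in the recorded 0 to 3+ score, by a Wilcoxon rank-sum test on patients with paired tissue. Keep the `--`, `-+`, `+-`, `++` table as description only, and note beside it that a tumour can remain `++` while its intensity changes. Complete loss will still be visible there as `+-`.

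The cost is one or two sentences of analysis wording. It needs no new assay, tissue or patients, because the score is already collected.
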